10.0 Data Safety Monitoring

Given that this will be a small pragmatic pilot study, data safety monitoring will be done by the study team. The neonatal research nurses/coordinator will monitor data quality, subject recruitment, accrual, retention, outcome and adverse event data, and procedures designed to protect the privacy of subjects on a monthly basis. Any AE or SAE will be immediately discussed as described above. The study team, consisting of neonatal research nurses, coordinators, and the PI, will meet every 6 months to review the above factors as well as the results of any related studies that may impact subject safety.

11.0 Study Withdrawal/Discontinuation

Infants may be withdrawn from the study at any time at the request of the parent(s). If withdrawn from the study, they will receive standard treatment for neonatal abstinence syndrome, consistent with the control group. Infants may also be withdrawn from the study if there is a change in clinical status rendering it necessary to deviate from the study protocol per physician discretion.

12.0 Statistical Considerations

Based on previous data a sample size of 108 per group would be necessary to have 80% power to detect a 5-day reduction in length of stay; this is not feasible for a single site trial. In order to better design a larger RCT, a pilot study will be conducted.

A sample size of 12 per group has been suggested as appropriate for pilot studies to evaluate feasibility and to estimate means and standard deviations.¹³ All calculations assume a two-sided two-sample t-test conducted at a 5% significance level. This pilot data will be necessary to design a larger scale randomized trial.

13.0 Statistical Data Management

Data management and interpretation

Data will be collected using prepared forms, then entered and managed using REDCap electronic capture tools hosted and managed by IUPUI Biostatistics. The REDCap platform is a secure, web-based application designed to support data capture for research studies, providing: 1) an intuitive interface for validated data entry; 2) audit trails for tracking data manipulation and export procedures; 3) automated export procedures for seamless data downloads to

common statistical packages and 4) procedures for importing data from external sources. Only IRB approved research team members will have access to the REDCap data platform. Each team's members will be granted access to the REDCap data system through a secure login. In the REDCap data platform, primary data and data backups are secured at separate Indiana University Data centers. Operating system security includes: secure logins, data encryption at rest, remote system logging and configuration and change management. Data backups are encrypted both in flight and at rest. Copies of data are replicated to the remote data center every 15 minutes. There are 100+ point-in-time copies of data available at any time. Disaster recovery has been tested and confirmed.

Performance Monitoring: Standard reports can be generated from the study database by the research office. These will include monthly reports that provide the number of infants enrolled, missing data, adherence to study protocols, and a variety of performance measures, including adverse events.

14.0 Privacy/Confidentiality Issues

Security measures to protect subject identities include the use of coded files to unlink research records from names and other identifiers, locked storage areas, and password-protected computer files. Subjects' names are linked to their IDs as noted above. Access to computer systems housing sensitive information is strictly regulated. Credentials permitting access to these systems are granted only to essential investigators and research personnel. All systems are updated with necessary security patches as they become available. Related hardware and back-up storage media are maintained in a secure environment to which only essential personnel have physical access. All consent and research procedures will be compliant with Subpart B of the Code of Federal Regulations Title 45, Part 46 - Protection of Human Subjects with Additional Protections for Pregnant Women, Human Fetuses and Neonates Involved in Research (66 FR 56778, Nov. 13, 2001).

15.0 Follow-up and Record Retention

The duration of the study will from be from enrollment through 4-8 weeks of age. The majority of the data collection and monitoring will be done during the initial hospital stay. Once the infant is discharged from the NICU, we plan to contact the parent via phone for follow-up to determine if the infant has required readmission to the hospital for any issues potentially related to neonatal abstinence syndrome in the first month of life. If the baby stays in the IU Hospital system after birth, the study team will look for recent appointments that may contain the follow up information.

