8.0 Study Calendar

Timeline	Birth	Admission to NICU	Treatment	Discharge	Follow-up
Study Procedures	Screening for potential eligibility based on opioid exposure	Determine eligibility and approach for enrollment	Follow treatment course	Final data collection on outcomes	Phone call/chart review) at 4-8 weeks of age to assess for re- admission
		Collect baseline maternal and newborn data	Monitor for protocol deviations, issues, AEs, SAEs	Confirm contact information for follow-up phone call	
		Randomize	Continue data collection		

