9.0 Reportable Events

An adverse event (AE) is defined as any untoward medical occurrence in a subject in the investigation. AEs must be assessed for expectedness, severity, attribution (relatedness to the study intervention), and seriousness by the investigator, or another qualified study team member as characterized below. AEs deemed related to the intervention must be reported as serious adverse events (SAEs) if they become serious (become life-threatening, result in death, or prolong hospitalization). Recording of such adverse events will start at the time of the study consent and will stop upon discharge from the hospital.

The following criteria will be used to define relatedness:

Definite: The AE is clearly related to the study intervention

Probable: The AE is likely related to the study intervention

Possible: The AE may be related to the study intervention

Unrelated: The AE is clearly not related to the study intervention

The severity of AEs will be described as:

Mild: asymptomatic or mild symptoms, no intervention indicated

Moderate: clinically significant requiring minimal noninvasive intervention

Severe: severe or medically significant but not immediately life-threatening, need for intensive, emergent, or invasive intervention

Life-threatening: life-threatening physiological consequences, need for intensive or emergent invasive intervention

Newborns with NAS are at risk of several complications related to their withdrawal symptoms. They may experience excessive weight loss in the first 1-2 weeks of life (>10% of their birth weight), they may have oromotor dysfunction and require supplement gavage feedings to support growth, and in rare cases, they can have seizures. Adverse events will be monitored monthly by the study team and collected in REDCap. Infants who receive morphine are at risk of over-sedation and decreased level of consciousness, as well as respiratory depression that can result in apnea. While this risk is mitigated by the fact that infants with NAS are opioid-tolerant, it remains a risk especially when escalating the dose. Per standard care, all infants receiving morphine remain on cardiopulmonary monitoring throughout their treatment.

Adverse Event monitoring will include:

- 1. Depressed level of consciousness
 - Grade 1: Decreased level of alertness

Grade 2: Sedation; slow response to stimuli; sleeping longer than expected or needing to be aroused at feeding times

Grade 3: Difficult to arouse

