Grade 4: Life-threatening consequences; coma; urgent intervention indicated Grade 5: Death

- 2. Other events classified as serious and unexpected
- 3. Other events resulting in death or classified as Serious or Related (to study procedures)

A depressed level of consciousness grades 1-3 will be considered an AE, while grade 4 will be considered a SAE. All SAEs and AEs reported during this study will be followed until resolution or until the investigator confirms that the AE/SAE has stabilized and no more follow-up is required. All deaths and SAEs that are at least possibly related and all unexpected SAEs will be

reported to the investigator within 24 hours of the study team becoming aware. An initial SAE form must be as complete as possible, including details of the current serious adverse event, including an investigator assessment of the causal relationship between the event and study procedures. Information not available at the time of the initial report must be documented on a follow-up SAE form. All unexpected SAEs will be reported to the IRB within 5 working days. The study team will begin tracking AEs and SAEs at the time of consent and will conclude tracking after the follow-up phone call has been made when the infant is 4-8 weeks of age.

We will not report deviations as clinical care is being followed. This is a pragmatic pilot trial that is not intended to alter the standard of care treatment. It is ideal that the morphine is dosed every 3 hours/FINN scores obtained for those on the standard arm. However, there will be times this does not occur, and it will not be considered a protocol deviation.

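### The follow-up call asks only about readmissions linked to NAS, by an undefined criterion, while the study calendar sets no cause limit and the end of adverse event tracking is contradictory

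*Combined protocol and SAP*

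**What the plan says.** Three sections of the protocol bear on what is learned about an infant after discharge.

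- **Section 15.0 (Follow-up and Record Retention)** describes the contact: "we plan to contact the parent via phone for follow-up". Its stated purpose is "to determine if the infant has required readmission to the hospital for any issues potentially related to neonatal abstinence syndrome", limited to the first month after birth. For babies who stay in the same hospital system there is a second source: "the study team will look for recent appointments that may contain the follow up information".
- **Section 8.0 (Study Calendar)** lists a phone call or chart review "at 4-8 weeks of age to assess for re- admission". It sets no limit on cause.
- **Section 9.0 (Reportable Events)** says of adverse event recording that it "will start at the time of the study consent and will stop upon discharge from the hospital". Later in the same section the study team "will conclude tracking after the follow-up phone call has been made when the infant is 4-8 weeks of age". The definition of an event is broad: "An adverse event (AE) is defined as any untoward medical occurrence in a subject in the investigation".

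Readmission is not among the outcomes in section 3.0, and section 12.0 plans no analysis of it. Section 5.0 hypothesises less morphine and a shorter stay with as-needed dosing. Blinding is not mentioned anywhere.

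**The concern.** If as-needed dosing sends infants home sooner, readmission is the natural counterweight, and it is the one event that the follow-up contact is set up to find. Section 15.0 filters that event when it is collected. Someone has to decide whether an admission might be linked to withdrawal. The protocol gives no criterion and does not say who decides.

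The judgement is not easy. The scoring tool in Appendix 1.0 includes poor feeding, loose stools, fever and fast breathing, all of which can have other causes in a young infant. The available informants are the parent and the study team reading records. Scheduled and as-needed dosing look different at the bedside, so both probably know the arm.

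An admission that is never asked about cannot be recovered at analysis. An admission that is recorded with its reason can be classified later. The pilot is meant to inform a larger trial, so an ambiguous readmission definition could also carry forward.

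**Working it through.** The plan states no figure on readmission, so there is none to reproduce. The check is a comparison of the text, followed by two short calculations for scale.

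**1. Scope, window and end of tracking**

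| Place | Events covered | Period |
|---|---|---|
| Section 8.0 | Readmission, no cause limit | Contact at 4-8 weeks of age |
| Section 15.0 | Readmission possibly linked to NAS | First month after birth |
| Section 9.0, opening paragraph | All adverse events | Consent to discharge |
| Section 9.0, later text | All AEs and SAEs | Consent until after the 4-8 week call |

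Sections 8.0 and 15.0 differ on cause and on period. The two statements in section 9.0 cannot both be followed. If the first governs, an admission thought unrelated to NAS has no described route into the data. If the second governs, it could be recorded as an adverse event. The only post-discharge sources described are still the call and the in-system record review, so capture depends on what the call asks. The seriousness criteria in section 9.0 name prolonged hospitalization but not readmission.

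**2. What the window leaves**

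Input: an average stay of 21.5 days among morphine-treated infants in 2018 (section 1.0).

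- First month taken as 30 days: 30 − 21.5 = 8.5, about 9 days after an average discharge.
- Contact at 4 weeks: 28 − 21.5 = 6.5 days after discharge.
- Contact at 8 weeks: 56 − 21.5 = 34.5 days after discharge.

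The periods differ several-fold, and a contact at 4 weeks comes before a 30-day month has ended. These figures are for an average stay; individual infants will vary.

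**3. What a filter could remove**

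Inputs: 24 infants (section 5.0); all-cause readmission risk p of 5%, 10% or 20%, **assumed**; share f passing the filter of 1 or one half, **assumed**. Expected recorded events = 24pf. Chance of recording at least one = 1 − (1 − pf)^24.

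| p | Expected, all recorded | Expected, half recorded | P(≥1), all | P(≥1), half |
|---|---|---|---|---|
| 5% | 1.2 | 0.6 | 0.71 | 0.46 |
| 10% | 2.4 | 1.2 | 0.92 | 0.71 |
| 20% | 4.8 | 2.4 | 0.995 | 0.92 |

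**4. What 12 per arm can show**

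Exact (Clopper-Pearson) 95% limits are 0-26.5% for 0/12 and 0.2-38.5% for 1/12. These overlap almost entirely. Losing one event changes the description of an arm, but no between-arm comparison of readmission is possible with or without the filter.

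**The case against.** The strongest reply is that section 15.0 states the purpose of a phone call and sets no counting rule. Readmission is not a listed outcome, the wording is inclusive, and section 9.0 already counts weight loss and feeding difficulty among the complications of withdrawal, so many doubtful admissions would pass. The calendar cell may simply be shorthand for section 15.0. Much of this stands, and it makes the point one of data-collection wording, not of analysis. It does not supply a criterion, and it does not remove the differences in window and in the end of adverse event tracking.

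Three stronger readings are tempting, and the documents do not support them.

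- *A reader might infer that the call is the only check after discharge.* The later text of section 9.0 tracks AEs and SAEs through the call without a cause limit. All-cause capture is unclear; it is not shown to be absent.
- *A reader might infer that staff who know the arm discard unrelated readmissions.* No section says who judges relatedness or that anything is discarded. Unblinded conduct is a fair inference from the two dosing schedules, but the person deciding could be the parent.
- *A reader might infer that a definite share of the safety signal is lost, or that one arm is favoured.* The documents give no readmission rate, and nothing in them fixes a direction of bias. The table above rests on assumed values.

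**Conclusion.** The point holds as a minor one. As written, section 15.0 can miss readmissions that section 8.0 would pick up, and section 9.0 does not settle whether they would be captured as adverse events. With 24 infants and an assumed all-cause risk of 5-20%, 1.2 to 4.8 events are expected. A filter that passed half of them would lower the chance of recording any from 0.71 to 0.46 at the low end and from 0.995 to 0.92 at the high end. This rests on the assumed risk and share, and on reading the trial as unblinded. It does not affect the feasibility outcomes in section 3.0 or any stated figure.

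**What to change.** Reword section 15.0 so that both the call and the chart review record every hospital readmission, for any cause, with its date and reason, up to the contact at 4-8 weeks of age. Keep the discharge and contact dates alongside, because the time observed after discharge will differ between infants. Report readmission descriptively by randomized arm. Show NAS-related readmission as a subset, classified afterwards by a criterion written in advance.

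Then reconcile sections 8.0, 9.0 and 15.0 so that they agree on scope, window and the end of adverse event tracking.

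The cost is one broader question on a contact already planned, plus small text edits. The downside is that a few clearly unrelated admissions will be counted in both arms; the recorded reason lets a reader see which they are.

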Appendix 1.0

Modified Finnegan Scoring Tool.

SYSTEM	SIGNS AND SYMPTOMS	SCORE	Ara					PNA				COMMENTS
	Continuous High Pitched (or other) Cry	2										Daily Weight:
	Continuous High Pitched (or other) Cry	3										
ŝ	Sleeps <1 Hour After Feeding	3										
ANC	Sleeps <2 Hours After Feeding	2										
URB	Sleeps <3 Hours After Feeding	1										
DIST	Hyperactive Moro Reflex	2										1
STEM	Markedly Hyperactive Moro Reflex	3										
SYS	Mild Tremors Disturbed	1										
inov	Moderate-Severe Tremors Disturbed	2	-		_			 	 			
NER	Mild Tremors Undisturbed	3										
RAL	Moderate-Severe Tremors Undisturbed	4			_	L						
ENTI	Increased Muscle Tone	2	_		_							
0	Excortation (Specific Area)	1										
	Myoclonic Jerks	3										
	Generalized Convulsions	5										
Å	Sweating	1										
ATOF	Fever 100.4*-101*F (38*-38.3*C)	1										
SPIR	Fever > 101°F (38.3°C)	2										
ES RE	Frequent Yawning (>3-4 times/interval)	1										
ANG	Mottling	1										
OMO	Nasal Stuffiness	1										
VAS	Sneezing (>3-4 times/interval)	1										
OLIC	Nasal Flaring	2										
TABC	Respiratory Rate >60/min	1										
W	Respiratory Rate > 60/min with Retraction	s 2										
GASTRO-INTESTIONAL DISTURBANCES	Excessive Sucking	1	1						1	1		1
	Poor Feeding	2										
	Requiritation	2			-							
	Projectile Vomiting	3										
	Loose Stools	2	1			1						
	Watery Stools	3										
	INITIAL S OF SCORER											
	INTIALO OF OOUNER						1					1

NEONATAL ABSTINENCE SCORING SYSTEM
